Study Protocol with Statistical Analysis Plan
SAFE Workplace Intervention for People With IDD

Official Title: Efficacy of the SAFE Program to Promote Preventative Behaviors of Airborne Diseases (COVID-19) and Improve Well-Being for People with Intellectual and Developmental Disabilities in the Workplace

NCT06112249

November 6, 2025

1) Abstract of the study

The purpose of this study is to examine the feasibility and efficacy of a systematic training approach targeting behaviors to increase safety and prevention of airborne diseases such as COVID-19 in the workplace for individuals with Intellectual and Developmental Disabilities (IDD). *This project is designed to determine proof of concept and proof of product for a peer support intervention, the **SAFE** program, to increase knowledge and safe workplace practices.* There is an identified immediate need for individuals with IDD to receive training in an accessible format. The **SAFE program** has been developed in an accessible format for those with IDD. It focuses on education regarding actionable behaviors that reduce the risk of acquiring and transmitting COVID-19 and other airborne diseases. The study will implement a peer-mediated and occupational therapy lead program, **SAFE**, to identify and address potential implementation issues and further refine the program curriculum. Additionally, the efficacy of the program on perceived safety and well-being, observable preventative behaviors and self-advocacy will be examined.

2) Protocol Title

Efficacy of the **SAFE** Program to Promote Preventative Behaviors of Airborne Diseases (COVID-19) and Improve Well-Being for People with Intellectual and Developmental Disabilities in the Workplace

3) Investigator

[name], OTR/L, BCP, FAOTA

[name]

4) Sponsor:

PA Department of Health

5) Objectives

It is hypothesized that the **SAFE program** will have a positive effect on perceived well-being and knowledge of the actionable behaviors for the prevention of COVID-19 and other airborne diseases. The program will have a larger effect on outcomes when provided using peer support compared to staff training. Individuals with IDD will demonstrate increased knowledge and safe behaviors after completing the **SAFE program**. Peer-interventionists will report perceived benefits and limitations of participating in training and providing peer-mediated travel training interventions to identify potential outcomes for future research.

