The research intends to answer these questions:

1. Does participation in the **SAFE program** increase perceived safety and well-being in the workplace for people with ASD and/or IDD?

SAFE Protocol

2. Does participation in the *SAFE program* increase knowledge of actionable behaviors to prevent transmission of airborne diseases (i.e. COVID-19) in the workplace for people with IDD?
3. When implemented through *peer support*, does the *SAFE program* have a larger increase in perceived well-being and knowledge of actionable behaviors to prevent transmission of airborne diseases (i.e. COVID-19) than when implemented through staff training and supports?

The research further intends to:

- Develop health communication messages related to safe interactions and the prevention of COVID-19 and other infectious airborne diseases for autistic adults
- Refine and expand the SAFE program based on stakeholder priorities and input Evaluate the SAFE program training with Autistic adults

Phase 2

1: Identify stakeholder priorities for additional health communication content related to staying safe from infectious airborne diseases.

2: Develop new content based on the identified needs and incorporate it into the SAFE program for individuals with IDD.

3: Pilot the new curriculum with direct care providers and refine materials based on feedback to ensure effectiveness.

6) Rationale and Significance

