We will use a questionnaire to assess knowledge of actionable behaviors to prevent COVID-19, which reflect the core components of the *SAFE program* (social distancing, proper use of PPE, personal hygiene practices, and self-advocacy in the workplace). We will also administer measures to determine the degree of self-advocacy and self-efficacy in the work place reported by staff and self-reported by participants. We will determine how well a participant follows workplace procedures. Data will be collected either in person or virtually both at pre-test and post-test for all outcome measures. Finally, we will assess perceived anxiety.

Phase 2

Focus Group Participation

Recruited and consented participants will take part in focus groups consisting of 5-10 people. These focus groups will be held in convenient, private locations such as agency centers or conducted via Zoom to ensure both accessibility and privacy for all participants. During the focus groups, participants will be presented with a summarized and accessible version of the SAFE program. After reviewing the material, participants will share their experiences, priorities, and concerns, specifically focusing on any important priorities that they feel are missing from the current SAFE program curriculum. Research staff will facilitate these discussions. Each session will be recorded and transcribed using Zoom built in features to accurately capture the data. Focus groups will last no longer than two hours. Participants will be compensated \$30 for their participation.

Content Development for the SAFE Program

- Once the focus group analysis is completed, research staff will proceed with the creation of new content for the SAFE program. The team will draft educational materials that address the priorities identified during the focus groups. The draft content will undergo a rigorous review process through an advisory board involving subject matter experts, stakeholders, and individuals with lived experiences to ensure the content's accuracy and relevance. **Five to ten stakeholders will review the new content developed for the SAFE program. They will receive the newly developed content and provide feedback on its accessibility, clarity, and overall engagement. The content will be sent via email, and stakeholders will be asked to provide their feedback either through email or during a scheduled group Zoom meeting.**

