Based on the feedback received, research staff will make any necessary revisions to ensure the materials are both effective and accessible.

Once finalized, the new content will be integrated into the existing SAFE program materials. Research staff will adapt the content into various formats, including written guides, videos, and infographics, to meet the diverse learning needs of participants.

Pilot Testing for Service Providers

- Research staff will recruit 5-10 staff members from a large service provider organization to participate in pilot testing of the training materials. This pilot testing will occur over a 1-2 month period, during which staff will be trained on the new SAFE materials and additional content. The trainings will occur using Zoom meetings. The training sessions will be conducted either in groups or individually, depending on scheduling availability. Feedback will be collected from participants through surveys, interviews, or debriefing sessions to evaluate the effectiveness of the training. The training feedback will be audio recorded to ensure that we capture all important information you share. The audio recordings will be transcribed by the project team using Zoom's transcription feature. By signing the consent form, you are giving permission to be recorded.
 - Only people working on this project will have access to the recordings.
 - Information and transcripts will be stored securely in locked filing cabinets or on password-protected computers.

Based on this feedback, research staff will refine the training materials and curriculum, making necessary adjustments to improve clarity, accessibility, and applicability. These

SAFE Protocol

trainings will not be recorded. Feedback will only be collected using FIM surveys, AIM surveys and exit interview.

Once these refinements are complete, the finalized curriculum will be prepared for broader implementation within service-based organizations that support individuals with IDD. Participants will receive \$50 for the training. Participant will receive \$25 after the first training sessions and an additional \$25 after completion.

Data Analysis. Descriptive statistics including mean, median, standard deviation, skewness, frequencies, and percentages will be computed on demographic and measures as appropriate. We will complete ANOVAs to determine if there were significant changes in scores on outcome measures within and between groups. We will use SPSS to complete the analyses.

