review codes, 2) identify areas of disagreement, 3) recode data until consensus is reached, and 4) collapse initial codes into a preliminary framework of interrelated themes. The transcripts will be reanalyzed until a final thematic structure is reached. The research team will implement a number of methodological actions to strengthen the data collection process and trustworthiness including reflexivity, triangulation, and stakeholder checks.

Demographics and Potential Moderators.

The research team, primary investigators or research assistant, will collect demographic data including age, gender, ethnicity, education, type of area lived in, and primary and other diagnosis. The demographic form is completed *only* during pre-test data collection. Additionally, we will track participants who acquire an infectious airborne disease (IAD) during the course of participation in the study. This is not considered a primary outcome as we are not able to incorporate contact tracing within the scope of this project. Therefore, it is unlikely that we can confidently identify whether the participant acquired the IAD in the workplace. We will rely on self or caregiver report to acquire this information. The process of collecting this information will help in determining if it is feasible to include this as an outcome in future research.

Primary Outcomes Measure will be collected by the research team, primary investigators or research assistant.

Workplace Health and Safety Assessment. The Workplace Health and Safety Assessment assesses *both* knowledge and actionable behaviors participants exhibit to prevent IADs. The items for the tool were developed from recommendations provided by the CDC to reduce exposure to IADs including use of personal protective equipment, personal hygiene and social distancing. The assessment includes 20 items and takes approximately 15-20 minutes to complete through both administrator observations in the workplace environment (8 items) and questions completed by the participant (12 items). Response options are “rarely, never, sometimes, most of the time, always” and are scaled from 1 to 5 respectively. A total raw score is provided for data analysis.

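### Six pre/post scales follow one primary-outcome line without ranking; no lead outcome is clearly identified, and no alpha, lead contrast or multiplicity rule is given

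*Combined protocol and SAP*

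**What the plan says.** The line that labels the primary outcome is in the Measures section: "Primary Outcomes Measure will be collected by the research team, primary investigators or research assistant". Six scales that yield questionnaire or rating scores follow it:

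1. Workplace Health and Safety Assessment (total raw score)
2. PROMIS General Self-Efficacy (T-score)
3. VocFit Safety Subscale (no analysis score stated)
4. Workplace Health and Safety Self-Advocacy Scale, WHSSS (no analysis score stated; described as both staff-reported and self-reported)
5. NIH Toolbox Perceived Stress (T-score)
6. PROMIS Anxiety Short Form 8 (T-score)

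No secondary-outcome heading closes the list. The only outcome expressly ruled out as primary is acquired infection: "This is not considered a primary outcome as we are not able to incorporate contact tracing within the scope of this project".

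On timing, Procedures says: "Data will be collected either in person or virtually both at pre-test and post-test for all outcome measures". On testing, Data Analysis says: "We will complete ANOVAs to determine if there were significant changes in scores on outcome measures within and between groups". It adds descriptive statistics and the software, and nothing else on inference.

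The aims are efficacy aims. The Abstract says: "Additionally, the efficacy of the program on perceived safety and well-being, observable preventative behaviors and self-advocacy will be examined". Question 1 asks whether the program will "increase perceived safety and well-being in the workplace for people with ASD and/or IDD". Question 2 asks about knowledge of preventive behaviors. Question 3 compares peer with staff delivery on well-being and knowledge, and Objectives predicts a direction: "The program will have a larger effect on outcomes when provided using peer support compared to staff training".

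**The concern.** The plan does not say which result decides each question. Three things follow if it is run as written.

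- With several scales and no ranking, one chance result could be reported as a primary finding. With mixed results, no rule says whether Question 1 or Question 3 was answered yes or no.
- Within-group tests stand beside between-group tests, so a pre/post change inside a SAFE arm could be read as efficacy although the control arm exists to rule that out.
- A three-arm omnibus test does not by itself compare peer with staff delivery, and no direct contrast is planned for Question 3.

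No scale is tied to perceived safety or to well-being. Procedures maps some constructs in part (knowledge, self-advocacy and self-efficacy, following workplace procedures) and ends with "Finally, we will assess perceived anxiety", but it does not say that anxiety stands for well-being.

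**Working it through.** **1. The plan's own sample figure.** Inclusion and Exclusion Criteria: 120 × (1 − 0.20) = 96, which reproduces the stated final sample. With three equal arms, 96 / 3 = 32 per arm. Other passages allow other sizes. Recruitment Methods gives 120 + 120 = 240 for the same 96, but 240 × 0.8 = 192, or 64 per arm. Study Timelines speaks of about 120 completing, or 40 per arm. Arm size hardly affects the error rates below (64 per arm: 27% to 17%).

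**2. Assumptions not in the documents.** No true effect; 0.05 per test; normal change scores; a common correlation between scales, varied from 0 to 0.9. For two time points, the group-by-time test equals a one-way F test on change scores (2 and 93 degrees of freedom).

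**3. Reading A: only the Workplace Health and Safety Assessment is primary.** One omnibus test gives 5%, or 2.5% with the pooled SAFE mean on the favorable side. No inflation arises. This scale covers knowledge and preventive behavior, so Question 1 and the well-being half of Question 3 are left without a primary measure.

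**4. Reading B: all six are primary.** For independent scales:

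- at least one significant omnibus test: 1 − 0.95^6 = 0.265
- the same with the pooled SAFE mean better than control: 1 − 0.975^6 = 0.141

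For correlated scales, 40,000 simulated null trials per setting (simulation error about 0.2 percentage points):

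| Correlation | Any significant F | And pooled SAFE better | And both SAFE arms better |
|---|---|---|---|
| 0 | 26.6% | 14.2% | 9.7% |
| 0.3 | 24.6% | 12.8% | 8.7% |
| 0.5 | 21.3% | 11.1% | 7.7% |
| 0.7 | 16.9% | 8.8% | 6.0% |
| 0.9 | 11.4% | 6.0% | 4.1% |

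A larger run of 300,000 trials at 0.7 gave 17.1% and 8.9%. An omnibus F has no direction, so the last two columns show what favoring SAFE is taken to mean. If WHSSS is scored separately for staff and self-report, there are seven tests: 1 − 0.95^7 = 30% for independent scales.

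**5. Adding the within-group tests.** Three arms × six scales = 18 pre/post tests. If nothing changes in any arm and the scales are independent, 1 − 0.95^18 = 60% give at least one significant result. With the omnibus tests added, simulation gives about 62% at correlation 0 and about 44% at 0.7. This counts either direction and includes the control arm.

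**6. Cost of adjusting.** Two lead outcomes × two contrasts = four tests. Holm's strictest step is 0.05/4 = 0.0125 across all four, or 0.05/2 = 0.025 within each question. For peer versus staff, 32 v 32, a two-sample t test has 62 degrees of freedom and noncentrality d × √(32/2) = 4d. The effect sizes d are assumed.

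| d | Power at 0.05 | at 0.025 | at 0.0125 |
|---|---|---|---|
| 0.8 SD | 88% | 81% | 73% |
| 0.5 SD | 50% | 39% | 29% |

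The difference detectable with 80% power at 0.0125 is 0.86 SD with 32 per arm (0.71 SD at 0.05) and 0.76 SD with 40 per arm.

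**The case against.** **The label is singular and sits directly above the Workplace Health and Safety Assessment.** A reader might infer that the plan has no primary outcome at all, or that its false-positive rate simply is 26% or 62%. The documents support neither. Reading A is natural, and under it the inflation figures do not apply. What stands is that no lead outcome is clearly identified, and that Reading A leaves the well-being questions without one.

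**The study is a proof of concept and is called a pilot.** That limits how serious the point is. It does not remove it, because the title, Abstract and Objectives state efficacy aims and a directional peer-versus-staff hypothesis.

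**Six is a count chosen for the calculation.** The perceptual survey items are in the same list and are also taken at baseline and one month. They are left out because they are compared through perceptual maps, not scale scores. The acceptability and feasibility measures serve a different aim. The figures are therefore illustrative of the plan, not a description of every planned test.

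**Adjusting across separate research questions is a matter of choice.** This is right. Holm across four tests is one defensible rule, and adjusting within each question is another. The defect is that no rule is stated.

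**The Workplace Health and Safety Assessment is not a ready-made lead outcome for Question 2.** This also stands. Question 2 asks about knowledge, while the total combines 8 items observed in the workplace with 12 answered by the participant. The response options place never after rarely on a 1 to 5 scale, so never scores higher as printed. People looking for work may enroll and may have no workplace in which to be observed.

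**Conclusion.** The concern holds in a limited form. The plan gives no clearly identified lead outcome, alpha, lead contrast or multiplicity rule. It lets within-arm change stand beside between-arm comparison and plans no direct peer-versus-staff test. These omissions are certain from the text.

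The size is conditional. If all six scales are primary at 0.05 each, with 32 per arm and correlation 0 to 0.7, 26% to 17% of null trials give at least one significant omnibus test (11% at correlation 0.9). In 14% to 9% the pooled SAFE mean is also better than control, or 10% to 6% if both SAFE arms must beat it. Counting pre/post tests in each arm gives about 62% to 44% for any significant result. If only the first scale is primary, the rate is 5% and the problem is one of coverage: Question 1 and half of Question 3 have no deciding measure. The documents do not settle which reading is meant. Of the numerical assumptions, only the total of 96 completers comes from them.

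**What to change.** Before analysis, amend the Measures and Data Analysis text:

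1. Base efficacy conclusions on between-arm comparisons of change. Report within-arm pre/post change descriptively.
2. Name one lead outcome per question from scales already collected. For Question 2, use the Workplace Health and Safety Assessment once three points are settled: correct the order of the first two response options; state whether the total or the 12 participant-answered items represent knowledge; and state how the 8 observed items are handled for participants without a job. For well-being, the sponsor chooses one scale.
3. On each lead outcome, test two planned contrasts, both SAFE arms versus control and peer versus staff, at a stated two-sided 0.05 with a stated multiplicity rule (for example Holm, within each question or across all four tests).
4. Label the remaining scales exploratory, with unadjusted 95% confidence intervals.

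No new data or participants are needed. The cost is that the other scales can no longer be claimed as primary successes, and each contrast loses power. Under the strictest option, peer-versus-staff power with 32 per arm falls from 88% to 73% for an assumed 0.8 SD, and from 50% to 29% for 0.5 SD. Adjusting within each question costs less.

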identified locations. All data collection activities will comply with the recommended social distancing requirements currently in place at the time.

Quantitative study measures will be implemented through the use of on-line REDCAP survey software and is available to interested individuals through an on-line link. Participants can complete the survey in any environment in which they have access to the Internet (i.e., public library; home; work). If the interested participant does not have a device to access the Internet and the survey or communicate with the researcher to indicate their responses, the primary researcher will meet them a place identified as convenient for the participant with the necessary equipment to complete the survey (i.e., laptop computer with Internet connectivity).

8) Prior Approvals

N/A

9) Study Design

Recruitment Methods

Recruitment will occur through local community partners, which include Philadelphia Independence Network, Community Integrated Services, Carousel Connection GRASP, ASERT, Philadelphia the Institute of Disability at Temple University, and the Philadelphia Area Charter School. We have an established relationship with all of these organizations. An introductory recruitment e-mail (see materials submitted with IRB protocol) will be sent to potential participants through the organization, which includes a link to the survey questions on REDCAP.

Phase 1

We intend to recruit 20 employed individuals with ASD and 20 employed individuals with IDD to complete in depth qualitative interviews, 100 employed individuals with ASD and 100 employed with IDD to complete **quantitative** perceptual mapping surveys. We will recruit 40 individuals 10 ASD 10 IDD, 10 vocational staff, and 10 from the project Advisory Board to conduct vector modeling analysis with and complete sample messaging. We aim to recruit at least 120 participants with ASD and 120 participants with IDD for the pilot SAFE program, which we anticipate will yield a total of 96 participants in the final sample when accounting for 20% attrition rates commonly identified in prior intervention studies of people with ASD and/or IDD.

Phase 2

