PROMIS General Self-Efficacy Item Bank. This measure assesses a person’s belief in their capacity to manage daily stressors and have control over meaningful events. Participants will complete the 10-question tool which is designed for people 18 years and older. It has established acceptable reliability and validity.⁸¹ The responses are on a 5 point scale from “I am a little confident” (1) to “I am very confident” (5) with higher scores reflecting greater general self-efficacy. A total standard T-score will be used to analyze the data.

VocFit Safety Subscale. The VocFit is an assessment tool used to measure the best fit for a worker with a job.⁸ The tool was specifically developed for individuals with developmental disabilities and has strong psychometric properties for this population.⁸² The VocFit safety subscale consists of 8 questions asking to what degree the participant demonstrates the ability to engage in safety protocol at their employment. The tool identifies the degree to which the participant is able to follow safety protocols and precautions in their work setting. The response options include “high”, “some”, and “low”.

Workplace Health and Safety Self-Advocacy Scale (WHSSS). This measure was adapted from employment-centered items on the Self-Determination and Self-Advocacy Questionnaire, which assesses the degree of self-advocacy in the workplace as reported by staff and self-reported by participants. The measure has ten questions and takes 5-10 minutes to complete. The modified WHSSS assesses the skills used to advocate for preventative practices for IADs in the workplace and the degree to which the person uses these skills. The response options range from “none of the time” (1) to “all of the time.”

Perceptual Survey Items. To assess perceptions of IADs and protective behaviors, we will utilize the perceptual mapping items developed in the formative phase. These will be determined at baseline and the one-month follow-up to see if perceptions have changed based on intervention content. We will be able to compare perceptual maps of interventions groups to see if specific messaging affected the relationship between the group and the target protective behavior.

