NIH Toolbox Item Bank/Fixed Form v2.0 – Perceived Stress (Ages 18+). This measure assesses “perceptions about the nature of events and their relationship to the values and perceived coping resources of an individual” for adults 18 years and older. This self-report measure has 14 items with a response range from “Never” (1) to “Very Often” (5). Higher scores reflect greater levels of perceived stress. The tool has established acceptable reliability and validity. A total standard T-score will be used to analyze the data.

PROMIS Item Bank v1.0 – Anxiety Short Form 8. This measure assesses anxiety for adults 18 years and older. This self-report measure has 8 items with a response range from “Never” (1) to “Very Often” (5). Higher scores reflect greater levels of anxiety. It has established acceptable psychometrics and is sensitive to change. A total standard T-score will be used to analyze the data.

Acceptability of Intervention Measure (AIM) and Feasibility of Intervention Measure (FIM). These measures were developed concurrently as the constructs are highly related. The AIM measures the acceptability of the intervention defined as “the perception among stakeholders that a given intervention is agreeable, palatable, or satisfactory” (Weiner et al., 2017). The FIM measures the feasibility of the intervention as defined as “the extent to which a new intervention can be successfully used or carried out within a given agency or setting (Weiner et al., 2017). Both tools demonstrated substantive and discriminant content validity and moderate to good test/re-test reliability. Preliminary research identified that the tools are sensitive to change in either direction. The tools take less than 5 minutes to complete and have a Flesch reading ease score at a 5th grade level. Response options range from completely disagree (1) to completely agree (5) with higher scores indicating greater acceptability or feasibility. A total raw score is provided.

Feasibility Data. The research team will evaluate the feasibility of the intervention and research methodology. Methods and benchmarks for evaluating feasibility include recruitment and retention rates, data about assessment procedures, feasibility survey

SAFE Protocol

questionnaires, and qualitative exit interviews of interventionists and participants. The participants will complete the Acceptability of Intervention measure (AIM) and the interventionist the Feasibility of Intervention Measure (FIM) at post-test 1.

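### The only printed scoring key for the Workplace Health and Safety Assessment puts rarely below never; check the stored codes and correct the key before totals are analysed

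*Combined protocol and SAP*

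**What the plan says.** The tool is the first measure described under the primary outcomes heading in the Measures section. It has 20 items: 8 are rated by an administrator who observes the participant at work, and 12 are answered by the participant. The response options are printed as "rarely, never, sometimes, most of the time, always", and they "are scaled from 1 to 5 respectively. A total raw score is provided for data analysis".

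No other part of the document gives a key, a recode or a reverse-scoring rule for this tool. Two other sections bear on the point:

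- **Resources and Settings:** "Quantitative study measures will be implemented through the use of on-line REDCAP survey software". The stored codes can therefore be checked there.
- **Data Analysis:** "We will complete ANOVAs to determine if there were significant changes in scores on outcome measures within and between groups". The total raw score would enter these analyses.

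**The concern.** The word respectively fixes the mapping: rarely = 1, never = 2, sometimes = 3, most of the time = 4, always = 5. The two lowest categories are out of frequency order. A participant who starts to take a precaution rarely, having never taken it, would lose a point.

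The protocol and the analysis plan are one document, so this sentence is the scoring specification an analyst would follow. The items were written for this purpose from CDC recommendations. Unlike several other measures in the section, the tool is described without any published scoring or psychometric support to fall back on. If the printed key was built into the form, into REDCap or into the scoring, the error is systematic and would carry into both the within-group and the between-group comparisons.

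**Working it through.** **Inputs from the Measures section.** Five options in the printed order, codes 1 to 5 in that order, and 8 observed plus 12 participant items. The stated item count reproduces: 8 + 12 = 20. With codes 1 to 5 the total runs from 20 to 100 under either key.

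**The two keys**

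| Option | Printed key | Frequency-ordered key | Printed minus ordered |
|---|---|---|---|
| never | 2 | 1 | +1 |
| rarely | 1 | 2 | -1 |
| sometimes | 3 | 3 | 0 |
| most of the time | 4 | 4 | 0 |
| always | 5 | 5 | 0 |

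Under the printed key a participant who answers never to all 20 items scores 40, and one who answers rarely to all 20 scores 20. The ordered key gives 20 and 40.

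**Score for each move, per item**

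| Move | Ordered | Printed |
|---|---|---|
| never to rarely | +1 | -1 |
| never to sometimes | +2 | +1 |
| rarely to sometimes | +1 | +2 |

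Moves among the three highest options are unaffected.

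**Bias in a between-arm difference.** From the last column of the first table, the mean item score is off by p(never) - p(rarely). For m items scored with the swapped key,

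bias in the total = m × (Δp_never - Δp_rarely),

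where Δp is the between-arm difference in the share of item responses in that category, or in its change from pre-test. The swap could affect one part of the tool or both, so m is 8, 12 or 20.

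**Unit illustration (assumed).** Suppose 10% of responses on each affected item move from never to rarely. The change in the total is:

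- m = 20: 20 × 0.10 = 2.0, so -2.0 instead of +2.0
- m = 12: 12 × 0.10 = 1.2, so -1.2 instead of +1.2
- m = 8: 8 × 0.10 = 0.8, so -0.8 instead of +0.8

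**One-step moves within the three lowest categories.** Let r be the share of such moves that are never to rarely, the rest being rarely to sometimes. The mean printed score per move is -r + 2(1 - r) = 2 - 3r, against 1 under the ordered key. The effect is overstated for r below 1/3, shrunk for r between 1/3 and 2/3, and reversed above 2/3.

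**Range of effect on an arm difference (assumed inputs).** The document gives no response data. The table takes several comparison-arm distributions, shifts a latent normal response by 0.3 SD, and swaps the key on all 20 items.

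| Comparison arm, never to always (%) | Ordered difference | Printed difference |
|---|---|---|
| 5 / 10 / 25 / 35 / 25 | +5.95 | +6.17 |
| 10 / 15 / 30 / 25 / 20 | +6.83 | +6.81 |
| 20 / 20 / 25 / 20 / 15 | +7.60 | +6.87 |
| 40 / 25 / 15 / 10 / 10 | +7.66 | +5.58 |
| 60 / 20 / 10 / 5 / 5 | +6.30 | +3.44 |
| 90 / 8 / 1 / 0.5 / 0.5 | +2.0 | -0.1 |

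In the last row Δp_never = -0.063 and Δp_rarely = +0.043, so the bias is 20 × (-0.063 - 0.043) = -2.1 points.

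**The case against.** The strongest reply is that this is a typing slip. The other three options run in order, and the other frequency scales in the section put the lowest frequency at 1: the self-advocacy scale, the Perceived Stress form and the Anxiety short form. A sentence that describes an instrument is not the instrument, and nothing shows that anyone scored data this way. This stands as the likeliest explanation. It does not make the check unnecessary, because the form and codebook are not in the document and the swap could sit in one part of the tool only. Even as a slip, it leaves a wrong key in the specification of a primary outcome.

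A second reply is that the effect is usually modest. In the assumed distributions above with 20% or fewer never answers, the arm difference changes by at most about 10% (7.60 to 6.87), in either direction. Material shrinkage needs never to be a very common answer, and the reversal shown needs 90%. This also stands, and it limits the likely harm.

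Third, this is one of several measures under the primary outcomes heading, and none is singled out. That is fair: being listed first does not give it primacy.

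Finally, the document does not state the direction of the score or whether any item is negatively worded, so a single ordered key for all 20 items rests on the printed plan. The plan does apply one scale to every item with no reverse scoring, so this is a point to confirm during the check and not a reason against it.

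**Conclusion.** The concern holds. The printed key is certainly out of order, and nothing else in the document corrects it. It is unlikely, though it cannot be ruled out, that data are scored that way.

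If the swap is only in the text, no score is affected. If it reached data capture or scoring, each never response is 1 point too high and each rarely response 1 point too low, and the arm difference is biased by m × (Δp_never - Δp_rarely). The size and sign of that bias cannot be known without response data. The illustrative distributions and the 0.3 SD shift are assumptions. That higher totals mean safer behaviour is inferred from always = 5.

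This should be fixed because it concerns the only scoring rule for a primary outcome and the check is cheap, not because bias has been shown.

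**What to change.** 1. Before scoring, check the option labels and stored codes on the form and in REDCap, separately for the 12 participant items and the 8 observed items. Confirm at the same time that no item is negatively worded.
2. Score the total with never = 1, rarely = 2, sometimes = 3, most of the time = 4, always = 5.
3. Only where data were captured under the printed key, swap codes 1 and 2 at item level, in the affected part only, before totals are computed. A blanket recode would damage items that are already coded correctly. If totals already exist, verify them and, if needed, rescore from the item data.
4. Correct the protocol sentence to match the key used in the analysis, and record any recode.

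The cost is one codebook check and one sentence. A recode, if needed, is one line and loses nothing provided item-level responses are kept; a total alone cannot be corrected afterwards.
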